4.1.10 Pregnancy Test

Urine or serum pregnancy tests will be required only for WOCBP. Testing will be done by a local or central laboratory as listed on the investigator's Form FDA 1572.

4.1.11 Hematology

Hematology studies must include complete blood count (CBC) with differential, including but not limited to white blood cell count, hemoglobin, hematocrit, platelet count, ANC, and absolute lymphocyte count (ALC). Testing will be done by a local or central laboratory as listed on the investigator's Form FDA 1572. Cycle 1 Day 1 hematology does not need to be repeated if screening hematology was done within 5 days.

4.1.12 Serum Chemistry

Chemistry will include albumin, ALP, ALT, AST, bicarbonate, blood urea nitrogen, bone-specific ALP, calcium, chloride, creatinine, C-terminal telopeptide, glucose, lactate dehydrogenase (LDH), magnesium, phosphate/phosphorus, potassium, sodium, total bilirubin, total protein, and uric acid. If an unscheduled ECG is done at any time, then an electrolyte panel (i.e., calcium, magnesium, and potassium) must be done to coincide with the ECG testing. Testing will be done by a local or central laboratory as listed on

Protocol: ACE-LY-001

the investigator's Form FDA 1572. Cycle 1 Day 1 serum chemistry does not need to be repeated if screening chemistry was within 5 days.

4.1.13 Hepatitis B and C Testing

Hepatitis serology testing must include hepatitis B surface antigen (HBsAg), hepatitis B surface antibody, anti-HBc, and hepatitis C virus (HCV) antibody. In addition, subjects testing positive for anti-HBc or HCV antibody must have respective PCR testing performed during screening (see Appendix 6 and exclusion criterion #12). Testing will be performed by local or central laboratory.

Subjects who are anti-HBc positive should have quantitative PCR testing for HBV DNA performed during screening and monthly thereafter. Monthly monitoring should continue until 12 months after last dose of study drug(s) for those on combination therapy and every 3 months for those on acalabrutinib monotherapy. Any subject with a rising viral load (above lower limit of detection) should discontinue study drug and have antiviral therapy instituted and a consultation with a physician with expertise in managing hepatitis B. Since IVIG may cause false positive hepatitis serology, monthly PCR testing is not required in subjects who are currently receiving or received prophylactic IVIG within 3 months before study enrollment and have a documented negative anti-HBc test before the initiation of IVIG therapy. PCR testing should be performed when clinically indicated (e.g., in the setting of rising transaminase levels).

Subjects with a known history of hepatitis C or who are hepatitis C antibody positive should be tested by quantitative PCR for HCV RNA during screening. Such subjects may be enrolled provided the quantitative PCR is negative (undetectable viral load). No further monitoring for HCV RNA during treatment is necessary if the initial PCR results are negative.

Refer to Section 3.11.1, and Appendix 6 regarding monitoring of subjects who are anti-HBc positive or hepatitis C antibody positive or who have a known history of HBV or hepatitis C.

4.1.14 Amylase and Lipase

Serum amylase and serum lipase testing will be done by a local or central laboratory as listed on the investigator's Form FDA 1572.

Protocol: ACE-LY-001

4.1.15 Urinalysis

Urinalysis includes pH, ketones, specific gravity, bilirubin, N-terminal telopeptide, protein, blood, and glucose. Testing will be done by a local or central laboratory as listed on the investigator's Form FDA 1572.

4.1.16 T/B/Natural Killer Cell Count

Flow cytometry testing will include CD3⁺, CD4⁺, CD8⁺, CD19⁺, and CD16/56⁺ cells. Testing will be done by a local or central laboratory as listed on the investigator's Form FDA 1572.

4.1.17 Serum Immunoglobulin

Testing for IgG, IgM, and IgA will be done by a local or central laboratory as listed on the investigator's Form FDA 1572.

4.1.18 Disease Markers

MM Subjects:

Testing for serum M-protein levels (by serum protein electrophoresis [SPEP] and serum immunofixation electrophoresis [SIFE]), serum-free light chains (SFLC), urine M-protein levels (by urine serum protein electrophoresis [UPEP] and urine immunofixation electrophoresis [UIFE]), and serum β2-microglobulin will be done by a local or central laboratory as listed on the investigator's Form FDA 1572.

WM Subjects:

Serum M-protein levels (by SPEP and IFE) will be done by a local or central laboratory as listed on the investigator's Form FDA 1572.

[figure not shown]
4.1.19 Skeletal Survey for MM Subjects

Standard lateral radiograph of the skull, anteroposterior and lateral views of the spine, and anteroposterior views of the pelvis, ribs, femur, and humerus are required at screening or baseline (i.e., before the first dose of study drug), at Cycle 12, and as clinically indicated. Radiographic imaging and analysis will be performed at the study center's local laboratory or other clinical laboratory listed on the investigator's Form FDA 1572.

Protocol: ACE-LY-001

4.1.20 Pharmacodynamics and Correlative Studies

Blood samples will be used for PD testing (e.g., BTK occupancy and B-cell activation), cytokine analysis, and for further characterization of circulating lymphocyte and myeloid cell subsets.

4.1.21 Pharmacokinetics

Refer to the laboratory manual for instructions on collecting and processing these samples. Testing will be performed at a central clinical laboratory. Leftover plasma samples may be used for exploratory acalabrutinib and ACP-319 metabolite analyses, or assessment of free (unbound) plasma concentrations of ACP-319 and M20 and/or measurement of plasma concentrations of α 1-acid glycoprotein. PK testing will be done for all subjects in Part 1 and for up to 24 subjects in Part 2 of the study as follows (Table 4-3).

Protocol: ACE-LY-001

Table 4-3. Pharmacokinetic Sample Schedule

| Day | Pharmacokinetic Timepoints |
|---------------------------------------------------------------------------|-----------------------------------------------------------------------------------------------------------------------------------------------------------------------------------|
| Cycle 1: Day 1, 28 | Up to 30 minutes before dosing and 0.5, 0.75, 1, 2, 4, and 6 hours after the morning dose of Day 1 and 28. Note the windows for these pharmacokinetic timepoints are ± 5 minutes. |
| Cycle 1: Day 8, 15, 22 | Up to 30 minutes before and 1 hour (± 5 minutes) after the morning dose on these days |
| Cycle 2: Day 15, 28 | Up to 30 minutes before the morning dose on these days |
| Cycles 3-4: Day 28 Up to 30 minutes before the morning dose on these days | |

All PK samples will be drawn relative to the morning dose.

4.1.22 Tumor Assessments

DLBCL (non-GCB and GCB), MCL, FL, CLL/SLL, RS, and WM:

A pretreatment CT scan with contrast (unless contraindicated) is required of the chest, abdomen, and pelvis and any other disease sites (e.g., neck) within 30 days before the first dose of study drug. A pretreatment positron-emission topography (PET)/CT scan is optional; however, if a recent PET/CT scan (within 90 days of the first dose) is available, the information will be recorded. Information on extranodal involvement will also be recorded.

For subjects with baseline (screening) extramedullary disease, on-treatment CT scans with contrast (unless contraindicated) of the chest, abdomen, and pelvis and any other disease sites (e.g., neck) will be done for tumor assessments at the end of Cycle 2 (±7 days), Cycle 4 (±7 days), and Cycle 6 (±7 days); every 3 cycles (12 weeks, ±7 days) through Cycle 18, and then every 6 cycles thereafter, or more frequently at investigator discretion. A CT scan is also done at the TT visit, if not done at the time of disease progression. Depending on the tumor type (eg MM, B-ALL, or WM in the absence of baseline extramedullary disease), on-study tumor assessments may be done by laboratory studies. Bone marrow and PET/CT are required for confirmation of CR per clinical guidelines (see Section 4.2).

Subjects should have radiographic tumor measurements done at the participating study center or an acceptable alternate imaging facility using an identical imaging protocol and similar equipment. The same imaging equipment should be used for all scans whenever possible. The same radiologist should be assigned to read all the scans for a given subject throughout the study.

Protocol: ACE-LY-001

In the event disease progression is suspected due to physical examination or laboratory test, a CT and/or PET/CT scan must be performed to confirm disease progression.

There must be radiographically measurable disease at screening (≥1 lymph node >2.0 cm in the longest diameter). If the sole lesion lies within the field of prior radiotherapy, there must be evidence of disease progression in that lesion.

Up to 6 measurable lymph nodes (only target lesions >1.5 cm in the longest diameter may be assessed), clearly measurable in 2 perpendicular dimensions, will be followed as target lesions for each subject. Measurable sites of disease should be chosen such that they are representative of the subject's disease. In addition, selection of target lesions should be from as disparate regions of the body as possible when these areas are significantly involved. If additional lesions are present but are not included in the target lesion assessment, they can be added as non-target lesions followed throughout the study. The cranial-caudal measurement of the spleen and longest diameter of the liver will be assessed at screening and all subsequent response evaluations.

MM

Baseline myeloma assessments will consist of:

- M-protein determination using the following procedures:
 - SPEP and SIFE
 - UPEP and UIFE (all using the same 24-hour urine collection)
- SFLC
- Plasmacytoma evaluation
- Bone marrow to quantify percent myeloma cell involvement (aspirate and biopsy required at baseline)
- Skeletal survey: lateral radiograph of the skull, anteroposterior and lateral views of the spine, and anteroposterior views of the pelvis, ribs, femora, and humeri
- β2-microglobulin

On-study myeloma assessments will consist of:

- SPEP and/or UPEP (if results were measurable at baseline); quantitative immunoglobulins if used to follow disease; immunofixation to confirm a CR
- SFLC
- Plasmacytoma evaluation (if only measurable disease at baseline)
- Bone marrow aspirate and/or trephine bone biopsy (to confirm a CR or if clinically indicated).

Protocol: ACE-LY-001

De-identified copies of all radiology results maybe requested by the sponsor.

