| CR with incomplete blood count recovery (CRi) | Recovery of platelets but <100,000/μL or ANC <1000/μL |
| Progressive disease | Increase of at least 25% in the absolute number of circulating or bone marrow blasts or development of extramedullary disease |

Abbreviations: ANC = absolute neutrophil count; B-ALL = B-cell acute lymphoblastic leukemia; CR = complete response; CRi = complete response with incomplete blood count recovery.

Protocol: ACE-LY-001

Table 4-8. Response Criteria for MM (incorporating EBMT and IMWG)

| Response Subcategory | Response Criteria ^a |
|-----------------------------------|----------------------------------------------------------------------------------------------------------------------------------------------------------------------------------------------------------------------------------------------------------------------------------------------------------------------------------------------------------------------------------------------------------------------------------------------------------------------------------------------------------------------------------------------------------------------------------------------------------------------------------------------------------------------------------------------------|
| Complete response (CR) | Negative immunofixation on the serum and urine and Disappearance of any soft tissue plasmacytomas and <5% plasma cells in bone marrow ^b |
| Stringent complete response (sCR) | CR as defined above plus Normal FLC ratio and Absence of clonal cells in bone marrow ^b by immunohistochemistry or immunofluorescence ^c |
| Near complete response (nCR) | Meeting the criteria for CR, except that the persistence of original monoclonal protein by immunofixation while absence of monoclonal protein on serum or urine protein electrophoresis |
| Very good partial response (VGPR) | Serum and urine M-component detectable by immunofixation but not on electrophoresis or ≥90% reduction in serum M-component plus urine M-component <100 mg per 24 h |

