| Partial response (PR) | ≥50% reduction of serum M-protein and reduction in 24-h urinary M-protein by ≥90% or to <200 mg per 24 h If the serum and urine M-protein are unmeasurable at baseline, a ≥50% decrease in the difference between involved and uninvolved FLC levels is required in place of the M-protein criteria. If serum and urine M-protein are unmeasurable at baseline, and serum free light assay is also unmeasurable, ≥50% reduction in plasma cells is required in place of M-protein, provided baseline bone marrow plasma cell percentage was ≥30%. In addition to the above listed criteria, if present at baseline, a ≥50% reduction in the size of soft tissue plasmacytomas is also required. |
| Minor response (MR) | MR includes subjects in whom some, but not all, criteria for PR are fulfilled providing the remaining criteria satisfy the requirements for MR. Requires all of the following: ○ ≥25% to ≤9% reduction in the level of serum monoclonal protein for ≥2 determinations 6 weeks apart ○ If present, a 50% to 89% reduction in 24-h light chain excretion, which still exceeds 200 mg/24 h, for ≥2 determinations 6 weeks apart ○ 25-49% reduction in the size of plasmacytomas (by clinical or radiographic examination) for ≥6 weeks ○ No increase in size or number of lytic bone lesions (development of compression fracture does not exclude response) |

Protocol: ACE-LY-001

Table 4-8. Response Criteria for MM (incorporating EBMT and IMWG)

| Response Subcategory | Response Criteriaª |
|------------------------------------------------------------------------------------------------------------------------------------------------------------------|--------------------------------------------------------------------------------------------------------------------------------------------------------------------------|
| Stable disease (SD) (not recommended for use as an indicator of response; stability of disease is best described by providing the time to progression estimates) | Not meeting criteria for CR, VGPR, MR, PR, or progressive disease. |
| Progression Subcategory | Progression Criteria ^d |
| Progressive disease ^a — To be used for | Laboratory or biochemical relapse or progressive disease: requires the occurrence of ≥1 of any of the following: |
| calculation of duration of response and progression-free survival | Increase of ≥25% from lowest response value in serum M-component and/or (the absolute increase must be ≥0.5 g/dL)e |

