| end points for all subjects including those in CR (includes primary | Urine M-component and/or (the absolute increase must be ≥200mg/24 h) |
| progressive disease and disease progression on or off therapy) ^g | Only in subjects without measurable serum and urine M-protein levels: the difference between involved and uninvolved FLC levels. The absolute increase must be >10 mg/dL |
| | Bone marrow plasma cell percentage: the absolute % must be ≥10% ^f |
| | Definite development of new bone lesions or soft tissue plasmacytomas or definite increase in the size of existing bone lesions or soft tissue plasmacytomas. |

EBMT (Bladé et al. 1998) and IMWG (Durie et al. 2006)

Abbreviations: CR = complete response; EBMT = European Group for Blood and Marrow Transplant; FLC = (serum) free light chains; IMWG = International Myeloma Working Group; MM = multiple myeloma; MR = minor response; nCR = near complete response; PR = partial response; sCR = stringent complete response; SD = stable disease; VGPR = very good partial response.

Note clarification to IMWG criteria for coding CR and VGPR in subjects in whom the only measurable disease is by serum FLC levels: CR in such subjects a normal FLC ratio of 0.26-1.65 in addition to CR criteria listed above. VGPR in such subjects is defined as a >90% decrease in the difference between involved and uninvolved free light chain FLC levels.

- a. All response categories require 2 consecutive assessments made at ≥4 weeks after the start of study therapy and any time before the institution of any new therapy after study therapy; CR and PR and SD categories also require no known evidence of progressive or new bone lesions if radiographic studies were performed. Radiographic studies are not required to satisfy these response requirements.
- b. Confirmation with repeat bone marrow biopsy not needed.
- c. Presence/absence of clonal cells is based upon the kappa/lambda ratio. An abnormal kappa/lambda ratio by immunohistochemistry and/or immunofluorescence requires a

Protocol: ACE-LY-001

minimum of 100 plasma cells for analysis. An abnormal ratio reflecting presence of an abnormal clone is kappa/lambda of >4:1 or <1:2.

- d. All relapse categories require 2 consecutive assessments made at any time before classification as relapse or disease progression and/or the institution of any new therapy.
- e. For progressive disease, serum M-component increases of ≥1 gm/dL are sufficient to define relapse if starting M-component is ≥5 g/dL.

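### Multiple myeloma: Section 4.1.22 schedules on-study plasmacytoma evaluation more narrowly than Table 4-8 needs to score partial response and to date progression

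*Protocol*

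**What the plan says.** Section 4.1.22 gives two lists for MM. The baseline list includes plasmacytoma evaluation without condition. The on-study list keeps it only under a condition: "Plasmacytoma evaluation (if only measurable disease at baseline").

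Table 4-8 (Section 4.2) uses plasmacytoma status in four categories, none restricted to subjects whose only measurable disease is a plasmacytoma:

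- Complete response (CR): "Disappearance of any soft tissue plasmacytomas".
- PR: "if present at baseline, a ≥50% reduction in the size of soft tissue plasmacytomas is also required". The table adds this to the M-protein, light-chain or plasma-cell criteria.
- Minor response: "25-49% reduction in the size of plasmacytomas (by clinical or radiographic examination) for ≥6 weeks".
- Progressive disease: "Definite development of new bone lesions or soft tissue plasmacytomas or definite increase in the size of existing bone lesions or soft tissue plasmacytomas". Any one of the listed progression findings is enough, and the table says this category feeds duration of response and progression-free survival (PFS).

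Section 4.2 tells the investigator to rate MM response by Table 4-8. Section 5.4.4 makes investigator-assessed ORR the primary efficacy endpoint and defines response through the same table.

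**The concern.** The response criteria call for a measurement that the MM assessment list does not schedule. The subjects concerned are those with a plasmacytoma at baseline who also have measurable M-protein or free light chains. Table 4-8 adds the plasmacytoma condition to their serum and urine criteria, yet the on-study list drops the evaluation because the plasmacytoma is not their only measurable disease.

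Two things are at stake. First, a PR could be recorded on M-protein alone while the plasmacytoma has not been re-measured. Second, plasmacytoma growth with falling M-protein could be picked up late or not at all, which lengthens duration of response and PFS. The direction of the ORR error depends on what the investigator does with the missing item. If shrinkage is assumed, ORR is too high. If PR is withheld because the condition cannot be checked, ORR may be too low.

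**Working it through.** **Step 1. Set the list against the table, by type of MM subject.**

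- Plasmacytoma is the only measurable disease: the on-study list schedules the evaluation, so list and table agree.
- Plasmacytoma plus measurable M-protein or light chains: PR needs at least 50% shrinkage and growth is progression, but the list schedules no evaluation. This is the gap.
- No plasmacytoma at baseline: PR needs nothing further, but a new plasmacytoma is progression and the list schedules no look for one.

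**Step 2. Look for the measurement elsewhere in the protocol.**

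- Section 4.1.22, first part, sets a CT schedule (end of Cycles 2, 4 and 6, and onward) for subjects with extramedullary disease at baseline. It stands under a heading that lists lymphomas, CLL/SLL, Richter's syndrome and WM, not MM. The same paragraph names MM among diseases that may be followed by laboratory studies, with a qualifier about absent baseline extramedullary disease that may attach to all the diseases named or to WM alone. Whether the CT schedule covers an MM subject with a plasmacytoma is therefore ambiguous.
- Appendix 5 says CT is not required in MM, but that schedule covers only Cycles >12, for subjects off ACP-319 for at least 3 cycles. It does not settle Cycles 1 to 12.
- Section 4.1.19 schedules skeletal surveys at baseline and Cycle 12. These are plain bone films and do not measure soft tissue plasmacytomas.
- Section 4.1.22 asks for CT and/or PET/CT when progression is suspected on examination or laboratory tests. That starts only after suspicion has arisen.
- Section 4.1.22 and Appendix 5 name marrow and PET/CT for confirming CR.
- Sections 4.1.7 and 4.1.23 provide symptom-directed and routine examinations, which can find palpable lesions.

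So PR and the timing of progression are the exposed items, and CR less so.

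**Step 3. Size.** Inputs: up to 12 subjects per histology (Section 3.0); in MM, 6 without and 6 with dexamethasone (Section 3.10.3). The number with a plasmacytoma is not given.

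The plan's own figures reproduce. Exact binomial 90% limits for x responses in n = 12 are

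- lower = Beta quantile 0.05 with parameters (x, n − x + 1)
- upper = Beta quantile 0.95 with parameters (x + 1, n − x)

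For x = 3 this gives 7.2% to 52.7%, and for x = 4 it gives 12.3% to 60.9%. Table 5-1 has 7% to 53% and 12% to 61%, and all 13 rows agree to rounding.

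One subject reclassified:

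- n = 12: 1/12 = 8.3 points. For example, 4/12 = 33% against 3/12 = 25%. At the 95% level that Section 5.4.4 uses, the intervals are 9.9% to 65.1% and 5.5% to 57.2%.
- n = 6: 1/6 = 16.7 points. For example, 2/6 = 33% (95% interval 4% to 78%) against 1/6 = 17% (0% to 64%).

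Range by assumed number affected, n = 12: none, 0 points; one, 8.3 points; two, 2/12 = 16.7 points.

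**The case against.** The strongest reply is that Table 4-8 governs. The investigator must rate by it, and it makes plasmacytoma shrinkage a condition of PR, so a PR called on an unexamined plasmacytoma misapplies the table. Section 4.0 also allows extra evaluations when clinically indicated. This stands as far as it goes: the protocol does not authorise such a PR. But a scoring rule does not produce the measurement, and the list that sites follow leaves it out.

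A second reply is that the parenthesis may have been meant as *only if measurable at baseline*. On that reading most of the PR problem goes away. New plasmacytomas, which count as progression, and any non-measurable ones, which CR requires to disappear, would still lack a scheduled evaluation. The line needs correcting either way.

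Three stronger readings are tempting, and the documents do not support them:

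- *That nothing else in the protocol supplies the measurement.* The extramedullary CT text can be read to include MM, Appendix 5 does not speak to Cycles 1 to 12, and examinations, CT on suspected progression and PET/CT for CR all exist.
- *That the same gap blocks PR in subjects followed by marrow plasma cells.* On-study marrow is allowed: "Bone marrow aspirate and/or trephine bone biopsy (to confirm a CR or if clinically indicated"). PR before Cycle 12 is therefore not blocked, and a missed PR would lower ORR.
- *That stable disease should also be recoded as not evaluable.* ORR is analysed on the All-treated population (Section 5.2), where neither category counts as a response, so the recoding would not change it.

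**Conclusion.** The contradiction is real but narrow. Section 4.1.22 and Table 4-8 disagree about when a plasmacytoma must be re-evaluated in MM. Followed as written, the MM list leaves PR and the timing of progression without a scheduled measurement in subjects who have both measurable M-protein or light chains and a baseline plasmacytoma. CR exposure is weaker. Whether the extramedullary CT schedule closes the gap depends on an ambiguous sentence.

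The effect is 8.3 ORR points per affected subject if 12 MM subjects were enrolled, and 16.7 points in a 6-subject subgroup. At 3 of 12 responders the 90% interval is already 52.7 − 7.2 = 45.5 points wide, so one subject does not transform what the cohort can show.

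Twelve is a ceiling, and the number enrolled is not stated. The MM cohort was closed to enrolment under Amendment 4. Misclassification also requires an M-protein response, a discordant plasmacytoma and no examination or imaging that reveals it. The number affected may be zero. A reader might infer that the reported MM response rate is inflated; the documents show only that it could be misclassified.

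**What to change.** 1. In the on-study MM list of Section 4.1.22, replace the condition so that plasmacytoma evaluation is done if one was present at baseline, or if a new one is suspected, by the method used at baseline (clinical or radiographic). Say in the same section whether the extramedullary CT schedule applies to MM, and align the Appendix 5 footnote.
2. State that a timepoint at which a baseline plasmacytoma was not re-evaluated is not evaluable for PR or better.
3. For MM subjects already assessed, apply that rule to the reported results. In ORR, count a response only from timepoints that meet it. In duration of response, start the clock at the first such timepoint. In PFS, flag timepoints recorded as progression-free without a plasmacytoma evaluation, because Section 5.4.4 censors at the last objective documentation of no progression. Report how many subjects are affected, including if there are none.

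The cost is one line of text, a short clarification and a coding rule. Extra examination or measurement falls only on MM subjects still in follow-up who had a baseline plasmacytoma or in whom a new one is suspected. The new line cannot recover past assessments, so the coding rule matters more for the data already collected. It may lower the MM response rate slightly.
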